10.4 Vital Sign Data

Vital signs are measured at screening, on Day –1, pre-dose on Day 1. Baseline values will be predose values taken prior to first IMP treatment on Day 1. If multiple pre-dose Day 1 values are recorded, the chronologically last recorded value prior to first IMP treatment on Day 1 will be taken to be the baseline value. If there are no pre-dose Day 1 values, then baseline values will be taken to be the last value recorded on Day –1; if Day –1 values are missing, then the last screening value will be taken to be the baseline value.

Descriptive statistics will be provided for change from baseline in vital signs parameters. Incidence of treatment-emergent potentially clinically significant vital sign results will also be summarized. Listings of potentially clinically significant abnormalities will also be provided. If vital sign assessments are repeated for the same visit, the last repeat values will be used for production of mean change from baseline. This is accomplished by sorting patient data by visit date and visit time (if applicable) within the same visit identification. Criteria for Identifying Vital Signs of Potential Clinical Relevance are provided in Appendices 2 and 3.

10.5 Physical Examination Data

Physical examination (PE) findings will be listed by subject. PE findings marked as clinically significant (CS) will be flagged in the listings.

Quabodepistat (OPC-167832)

Study 323-201-00007

10.6 Electrocardiogram Data

Electrocardiogram measurements (will include HR, PR, QRS, RR, QT, QTcF, QTcB) and mean changes from baseline will be summarized by part and time point. The incidence of potentially clinically significant changes and abnormalities in ECG evaluations will be summarized. Electrocardiogram data will be presented in listings. In ECG listings, abnormal will also indicate whether CS or not. For ECG assessments, baseline is defined as the average of triplicate (if not collected as triplicate, then single, or duplicate values will be averaged) ECG values collected at check-in for each Part. If there are two or more sets of ECG (check-in) evaluations prior to first IMP dosing, the last set of triplicate (or duplicate or single, as applicable) will be averaged for presenting as the baseline values (whether these are scheduled or unscheduled). Predose ECGs will be reported as predose and are not part of the baseline assessments.

If the baseline value is missing, it will not be imputed.

ECG parameter values will be reported as received in the raw data. ECG data will be reported out in listings, with the actual value and change-from-baseline value included in the listing.

Averaged ECG parameters will be rounded down to the nearest integer for easy interpretability.

10.7 Suicidality Monitoring

Suicidality monitoring will be conducted only in subjects enrolled in Part 2 and at the time points described in the SoA ([Table 1.3-2 of the protocol](#)).

The “Baseline/Screening” version of the C-SSRS will be completed at screening. This will be the baseline assessment for the C-SSRS.

The “Since Last Visit” version will be completed at all other specified visits (including ET, if applicable).

The “Baseline/Screening” version be used to assess Suicidal Ideation and Suicidal Behavior in both the subjects' lifetime and within the past 12 months prior to screening. There are a maximum of 19 items to be completed: 7 required, 10 potential additional items if there is a positive response to a required item, and 2 items for suicide/suicide behavior present during the interview. The C-SSRS uses dichotomous scales (ie, yes or no), Likert scales, and text or narrative to further describe the thoughts or behaviors.

The C-SSRS data will be analyzed for evidence of any treatment-emergent issues related to suicidal ideation or behavior. The incidence of suicidality, suicidal behavior, and

Quabodepistat (OPC-167832)

Study 323-201-00007

suicidal ideation will be summarized by treatment group and visit. No inferential statistical analyses will be performed. C-SSRS data will be listed.

10.8 Potential Serious Hepatotoxicity

According to FDA Guidance, laboratory measurements that signal the potential for drug-induced liver injury (DILI) will be reported. An incidence table and a listing will be provided for subjects who meet one or combinations of following criteria:

- 1) ALT or AST $\geq 3 \times$ upper limit of normal (ULN) (or baseline value for subjects with abnormal baseline)
- 2) increase in bilirubin $\geq 2 \times$ ULN (or baseline value for subjects with abnormal baseline)

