- Congenital anomaly/birth defect.
- Other medically significant events that, based upon appropriate medical judgment, may jeopardize the subject and may require medical or surgical intervention to prevent one of the outcomes listed above, eg, allergic bronchospasm requiring intensive treatment in an emergency room or home, blood dyscrasias or convulsions that do not result in hospitalization, or the development of drug dependency or drug abuse.

Nonserious AEs are all AEs that do not meet the criteria for a “serious” AE.

Adverse Events of Special Interest (AESIs): A noteworthy event for the particular IMP or class of products that a sponsor may wish to monitor carefully. All AESIs are to be reported as immediately reportable events (IREs). No AESIs have been identified for the IMP to be administered during this trial.

Immediately Reportable Event:

- Any SAE.
- Potential serious hepatotoxicity (see [Section 8.6.6](#)).
- Any AE related to occupational exposure (eg, an investigator getting a skin rash after exposure to a medication). Non-subject AEs would not be recorded on the eCRF form but must be recorded on an IRE form to the sponsor.
- Pregnancies are also defined as IREs. Although normal pregnancy is not an AE, pregnancy of a trial subject will mandate trial intervention discontinuation and pregnancy of either a subject or a subject's partner must be reported on an IRE form and the Pregnancy Surveillance Form(s) to the sponsor. This includes pregnancy of the subject or the partner of the subject. Pregnancy will only be documented on the AE eCRF if the pregnancy occurs in a female subject and there is an abnormality or complication (see [Section 10.3](#)).

Clinical Laboratory Test Value Changes: It is the investigator's responsibility to review the results of laboratory tests for each individual subject as they become available. This review will be documented by the investigator's dated signature on the laboratory report. The investigator may repeat the laboratory test or request additional tests to verify the results of the original laboratory tests. If this laboratory value is considered medically relevant (ie, clinically significant) by the investigator (subject is symptomatic, requiring corrective treatment or further evaluation), or if the laboratory value leads to discontinuation, and/or fulfills a seriousness criterion, this is considered an AE.

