8.6.6 Potential Serious Hepatotoxicity

For a subject who experiences an elevation in AST or ALT that is ≥ 3 times the upper limit of normal (ULN), a total bilirubin level should also be evaluated. If the total bilirubin is ≥ 2 times the ULN, complete an IRE form with all values listed and report as an AE in the eCRF. Details regarding the follow-up of IREs are included in [Section 8.6.8.2](#).

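### SAP 10.8 sets higher liver-test thresholds than Protocol 8.6.6 for subjects with abnormal baselines, and its bilirubin wording is ambiguous, so a protocol hepatotoxicity case can be missing from, or misclassified in, the liver-injury table

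*SAP*

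**What the plan says.** Protocol 8.6.6 works in two steps. An AST or ALT of at least 3 × ULN calls for a total bilirubin. Then: "If the total bilirubin is ≥ 2 times the ULN, complete an IRE form with all values listed and report as an AE". Both elements are needed, both are multiples of ULN, and neither is adjusted for baseline. Protocol 8.6.1 lists "Potential serious hepatotoxicity" among the immediately reportable events (IREs).

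SAP 10.3 promises an incidence table and a listing for potential serious hepatotoxicity, under the protocol's name for the event, and refers to SAP 10.8 for the criteria. SAP 10.8 covers "subjects who meet one or combinations of following criteria". The criteria are:

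- ALT or AST at least 3 × ULN, with the qualifier "or baseline value for subjects with abnormal baseline";
- "increase in bilirubin" of at least 2 × ULN, with the same qualifier.

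Under SAP 10.3 the laboratory baseline is Day −1, or screening if Day −1 is unavailable.

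**The concern.** A reader will expect the table to reconcile with the IRE forms, since the event has the same name in both documents. Two features of SAP 10.8 can prevent that.

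- **Baseline clause.** If it means 3 or 2 times the baseline value, the threshold rises for anyone who starts above ULN.
- **Bilirubin wording.** It does not say whether a value of 2 × ULN is enough or a rise of 2 × ULN is needed.

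Safety and tolerability is the secondary objective, and this is the only table planned specifically for liver-injury cases under itraconazole and carbamazepine. A case could be absent from it, or appear under one criterion only, while an IRE form exists for the same subject. The programmer would also have to choose between readings that give different tables.

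**Working it through.** The documents give no figure to reproduce, so the check compares the two rules directly.

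**Notation.** All values are in multiples of ULN. T0 and B0 are baseline transaminase and total bilirubin; T and B are on-treatment values. *Abnormal* is taken to mean above ULN.

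**Protocol rule.** A case if T ≥ 3 and B ≥ 2.

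**SAP rule.** Listed if criterion 1 or criterion 2 is met. Three readings are possible:

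- (a) Multiples of baseline, bilirubin as a level: T ≥ 3 × max(1, T0), or B ≥ 2 × max(1, B0).
- (b) As (a), but bilirubin as a change: B − B0 ≥ 2 × max(1, B0).
- (c) Literal baseline: for an abnormal baseline, the baseline value itself is the threshold.

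**When a protocol case is absent altogether**

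- If T0 ≤ 1, criterion 1 is T ≥ 3, which every protocol case meets through its triggering transaminase. None is absent under any reading.
- Under (a), absence requires 3 ≤ T < 3 × T0 and 2 ≤ B < 2 × B0. Both baselines must be abnormal.
- Under (b), absence requires 3 ≤ T < 3 × T0 and 2 ≤ B < B0 + 2 × max(1, B0). An abnormal transaminase baseline is enough.
- Under (c), none is absent for baselines up to 2.5, the range checked. But an unchanged abnormal baseline would then be flagged.

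**Worked examples.** The first four have on-treatment T = 4.0 and B = 2.2, and each is a protocol case.

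| T0, B0 | T, B | Reading (a) | Reading (b) |
|---|---|---|---|
| 1.5, 1.2 | 4.0, 2.2 | 4.0 < 3 × 1.5 = 4.5; 2.2 < 2 × 1.2 = 2.4: absent | 4.0 < 4.5; rise 1.0 < 2.4: absent |
| 1.5, 0.6 | 4.0, 2.2 | 4.0 < 4.5; 2.2 ≥ 2: bilirubin only | 4.0 < 4.5; rise 1.6 < 2: absent |
| 0.8, 1.2 | 4.0, 2.2 | 4.0 ≥ 3; 2.2 < 2.4: transaminase only | 4.0 ≥ 3; rise 1.0 < 2.4: transaminase only |
| 0.8, 0.6 | 4.0, 2.2 | 4.0 ≥ 3; 2.2 ≥ 2: both | 4.0 ≥ 3; rise 1.6 < 2: transaminase only |
| 0.8, 0.6 | 3.5, 1.0 | 3.5 ≥ 3: listed, though not a protocol case | the same |

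The last row shows the opposite direction: with normal baselines the SAP table is the broader of the two.

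**Grid check.** Baselines ran from 0.3 to 2.5 and on-treatment values from 0.3 to 8.0, in steps of 0.1. Protocol cases absent from the SAP table:

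| Baseline | Reading (a) | Reading (b) |
|---|---|---|
| Transaminase normal, bilirubin normal | 0 of 199,104 | 0 of 199,104 |
| Transaminase normal, bilirubin abnormal | 0 of 373,320 | 0 of 373,320 |
| Transaminase abnormal, bilirubin normal | 0 of 373,320 | 18,720 of 373,320 |
| Both abnormal | 86,400 of 699,975 | 183,600 of 699,975 |

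These are counts of grid points. They show where the rules part, not how often a subject would fall there.

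**Can such baselines occur?** Protocol 5.2.1 asks for good health judged partly on serum chemistry. Protocol 5.2.2 excludes clinically significant hepatic disease and hepatitis. Neither sets a numeric ALT, AST or bilirubin limit; the only numeric limits on safety laboratory values are hematologic and apply to Part 2. Abnormal baselines are therefore unlikely but not ruled out.

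**The case against.** The case for leaving SAP 10.8 alone is substantial.

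- **Breadth.** Either criterion alone is enough, so every protocol case whose triggering transaminase was normal at baseline is listed, however the bilirubin line is read. This stands. A reader might infer that the SAP rule is less sensitive across the board; the documents do not support that. It also does not settle the matter, because a listed subject can still be missing from the combined category, which is the one that corresponds to the IRE.
- **Other records.** Protocol 8.6.6 requires an IRE form and an AE entry. The DAIDS rows in SAP Appendix 2 use ULN multiples without baseline adjustment, and Grade 2 starts at 2.5 × ULN for ALT and AST and 1.6 × ULN for total bilirubin. Every protocol case is therefore at least Grade 2 on both tests. This stands: a reader might infer that the case disappears from the trial's safety reporting, and it does not.
- **Undeclared change.** A reader might infer that SAP Section 15, which lists no changes, is wrong. That is weak. Protocol 8.6.6 is a reporting rule for the site, and Protocol 9.4.3.2 plans no liver-injury table, so SAP 10.8 adds an analysis.
- **Benign reading.** The bilirubin line may simply mean a raised level; the protocol itself speaks of an elevation in AST or ALT and means a level. That is plausible, but it leaves the baseline clause, and the text should not depend on a guess.

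**Conclusion.** The concern holds in limited form. SAP 10.8 is broader than Protocol 8.6.6 when baseline transaminases are normal. It is stricter for abnormal baselines if the clause means multiples of baseline. A protocol case can then be absent from the liver-injury table and listing when the baseline transaminase is abnormal and either baseline bilirubin is also abnormal or the bilirubin line is read as a change. It can be counted as transaminase-only when only baseline bilirubin is abnormal, or with normal baselines on the change reading.

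The expected size is small: 24 healthy subjects, a narrow band of values, and a consequence confined to one table and its listing. The documents give no rate of abnormal baselines. If 5% to 15% were assumed, 24 × 0.05 = 1.2 and 24 × 0.15 = 3.6, or about 1 to 4 subjects. A reader might take that as the number of missed cases, but it counts only abnormal baselines; an omission also needs on-treatment values that meet the protocol rule and fall short of both SAP thresholds. The conclusion rests on reading (a) or (b); under the literal reading (c) no case is lost.

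**What to change.** In SAP 10.8, tabulate and list for every subject, whatever the baseline: AST or ALT ≥ 3 × ULN; total bilirubin value ≥ 2 × ULN; and both together, matching Protocol 8.6.6. Delete the words that make the bilirubin criterion an increase. If a baseline-adjusted view is wanted, add it as a separate row for subjects with an abnormal baseline, and state that it uses multiples of the baseline value.

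With the ULN-only combined row in place, no protocol case can be missed under any of the three readings. The cost is a few lines of SAP text and a little programming; Protocol 8.6.6 is untouched. The drawback is that subjects with raised baseline values may be listed more readily, which the additional row would help to interpret.

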10.9 Other Safety Data

Not applicable.

11 Pharmacokinetic Analyses

OPC-167832 plasma concentrations will be listed by subject and summarized using descriptive statistics (N, mean, median, standard deviation, percentage coefficient of variation, minimum, and maximum) by treatment and timepoint. The trough plasma concentration of itraconazole, hydroxy-itraconazole, and carbamazepine will be listed by subject and summarized using descriptive statistics, as applicable.

Noncompartmental PK analysis will be performed to estimate the PK parameters for OPC-167832.

The PK parameters that will be estimated are: C_{\max} , AUC_t , AUC_{∞} , time to maximum (peak) plasma concentration (t_{\max}), apparent clearance of drug from plasma after extravascular administration (CL/F), body weight normalized CL/F/BW, terminal phase elimination half-life ($t_{1/2,z}$). Other PK parameters, including those for metabolites, may be reported depending on the concentration data collected. Pharmacokinetic parameters will be summarized by treatment and timepoint using the same descriptive statistics as for concentrations plus geometric mean and geometric % CV. Values of t_{\max} will be summarized as median, minimum, and maximum.

Quabodepistat (OPC-167832)

Study 323-201-00007

11.1 Statistical Analyses of Primary Pharmacokinetic Endpoints

The effect of itraconazole or carbamazepine administration on the single-dose PK of OPC-167832 will be assessed using the primary PK parameters of OPC-167832: C_{\max} , AUC_t , and AUC_{∞} in the presence and absence of either itraconazole or carbamazepine.

Statistical analyses will be performed using the log-transformed PK parameters. The magnitude of the DDI will be assessed by computing the ratio of the geometric means of the OPC-167832 + potentially interacting drug versus OPC-167832 alone and the corresponding 90% confidence intervals (CIs) based on the log-transformed data.

An analysis of variance will be performed on the log-transformed PK parameters C_{\max} , AUC_t , and AUC_{∞} for OPC-167832 and/or its metabolites using the MIXED procedure in SAS for each part separately. The mixed-effects linear model for each PK parameter will include treatment (OPC-167832 + potentially interacting drug [test] and OPC-167832 alone [reference]) as a fixed effect and subject as a random effect. From each analysis, mean differences between the treatments OPC-167832 + potentially interacting drug and OPC-167832 alone and the 90% CI for the differences will be derived. The antilog of the differences will then provide an estimate of the geometric mean ratios (GMR; OPC-167832 + potentially interacting drug/OPC-167832 alone), and the antilog of the confidence limits will provide the 90% CIs (to at least 2 decimal places) for the GMRs.

SAS code for these analyses are outlined in [Appendix 6](#).

11.2 Statistical Analyses of Secondary Pharmacokinetic Endpoints

Not applicable.

11.3 Technical Details of Pharmacokinetic Statistical Analyses

Not applicable.

12 Pharmacodynamic Analyses

Not applicable.

14 Interim Analysis

None.

Quabodepistat (OPC-167832)

Study 323-201-00007

15 Changes in Planned Analysis

None.

Quabodepistat (OPC-167832)

Study 323-201-00007

16 References

- 1 United States Department of Health and Human Services, Division of AIDS, National Institute of Allergy and Infectious Diseases, National Institutes of Health. Division of AIDS (DAIDS) Table for Grading the Severity of Adult and Pediatric Adverse Events; 2017 (version 2.1).

17 Document History

Dates/Author	Description of Updates	Version	Document Updates
26 September 2022/ CCI [REDACTED]	draft	1.0	Not Applicable
25 January 2023/ CCI [REDACTED]	draft: 
 1) updated Appendix 1. Criteria now includes only parameters relevant to the study. 2) updated Appendix 2. The entire DAIDS table has been included as Appendix 2. 3) included QTxx > 480 msec (males and females) criterion for QT, QTcF and QTcB in Appendix 5. 4) clarified collection of relatedness of adverse events to IMP and its components. 5) Other minor updates to text for greater clarity and readability. 	1.1	Applied.
13 March 2023/ CCI [REDACTED]	Final version: 1) clarifications to text	1.0	

OPC-167832

Study 323-201-00007

Appendix 1 Definition of Grades in Serum Chemistry, Hematology and Urinalysis Lab Test Results in the Division of AIDS (DAIDS) Table for Grading the Severity of Adult and Pediatric Adverse Events

The table below contains reference to the criteria provided in the DAIDS table. The DAIDS table v2.1 is attached as [Appendix 2](#) to this SAP.

Protocol Assessment	DAIDS Grading Table Row(s)	Page in DAIDS grading tables
Hematology		
Hemoglobin	Hemoglobin, Low (≥ 13 years of age (female only)	29
	Hemoglobin, Low (≥ 13 years of age (male only)	29
Hematocrit	-	-
Mean corpuscular hemoglobin concentration	-	-
Mean corpuscular volume	-	-
RBC count	-	-
WBC count (absolute and differential)	WBC, Decreased	30
Platelets	Platelets, Decreased	30
Serum Chemistry		
Alkaline phosphatase	Alkaline phosphatase, High	25
Alanine aminotransferase	ALT or SGPT, High	25
Aspartate aminotransferase	AST or SGOT, High	25
Bilirubin, total (with reflex if elevated)	Total bilirubin, High	25
Blood urea nitrogen	-	-
Calcium	Calcium, High	26
	Calcium, Low	27
	Calcium (ionized), Low	28
Cholesterol	Cholesterol, Fasting, High	27
Creatinine	Creatinine, High	26
	Creatinine Clearance or eGFR, Low	26
Gamma glutamyl transferase	-	-
Glucose	Glucose, Fasting, High	26
	Glucose, Nonfasting, High	26
	Glucose, Low	27
Lactate dehydrogenase	Lactate, High	27
Magnesium	Magnesium, Low	27
Potassium	Potassium, Low	27

OPC-167832

Study 323-201-00007

	Potassium, High	27
Protein, total	-	-
Sodium	Sodium, High	28
	Sodium, Low	28
Triglycerides	Triglycerides, Fasting	27
Urinalysis		
Glucose or glycosuria	Glycosuria	31
Blood or hematuria	Hematuria	31
Protein or proteinuria	Proteinuria	31
Drug screen	-	-
Additional Tests		
Urine or serum pregnancy test	-	-
Follicle-stimulating hormone for post-menopausals	-	-
Serology (hepatitis B surface antigen, hepatitis C antibodies, human immunodeficiency virus)	-	-

OPC-167832

Study 323-201-00007

Appendix 2**Division of AIDS (DAIDS) Table for Grading the Severity of Adult and Pediatric Adverse Events (Corrected Version 2.1, July 2017)**

Glossary and Acronyms	
Acronym	Definition
AE	Adverse event; Any unfavorable and unintended sign (including an abnormal laboratory finding), symptom, or disease temporally associated with the use of a medical treatment or procedure regardless of whether it is considered related to the medical treatment or procedure.
ALT (SGPT)	Alanine aminotransferase (serum glutamic pyruvic transaminase)
ANC	Absolute neutrophil count
AST (SGOT)	Aspartate aminotransferase (serum glutamic-oxaloacetic transaminase)
AV	Atrioventricular
Basic Self-care Functions	Adult : Activities such as bathing, dressing, toileting, transfer or movement, continence, and feeding. Young Children : Activities that are age and culturally appropriate, such as feeding one's self with culturally appropriate eating implements.
BMI z-score	Body mass index z- score; A body reference norm. Specifically, the number of standard deviations a participant's BMI differs from the average BMI for their age, sex, and ethnicity.
BMD t-score	Bone mineral density t-score; The number of standard deviations above or below the mean bone mineral density of a healthy 30 year old adult of the same sex and ethnicity as the participant.
BMD z-score	Bone mineral density z-score; The number of standard deviations a participant's BMD differs from the average BMD for their age, sex, and ethnicity.
BPAP	Bilevel positive airway pressure; A mode used during noninvasive positive pressure ventilation.
Chemical Pregnancy	A pregnancy in which a positive pregnancy test is followed by a negative pregnancy test without evidence of a clinical pregnancy loss.
CNS	Central nervous system
CPAP	Continuous positive airway pressure
DAERS	DAIDS Adverse Experience Reporting System; An internet-based system developed for clinical research sites to report Expedited Adverse Events (EAEs) to DAIDS. It facilitates timely EAE report submission and serves as a centralized location for accessing and processing EAE information for reporting purposes.
Disability	A substantial disruption of a person's ability to conduct normal life functions
ECG	Electrocardiogram
eGFR	Estimated glomerular filtration rate
Hospitalization	Does not include the following hospital admissions: under 24 hours, unrelated to an adverse event (eg, for labor and delivery, cosmetic surgery, social or administrative for temporary placement [for lack of a place to sleep]), protocol-specified, and for diagnosis or therapy of a condition that existed before the receipt of a study agent and which has not increased in severity or frequency.

OPC-167832

Study 323-201-00007

Glossary and Acronyms	
Acronym	Definition
INR	International normalized ratio
Intervention	Medical, surgical, or other procedures recommended or provided by a healthcare professional for the treatment of an adverse event.
IV	Intravenous
IVIG	Intravenous immune globulin
LDL	Low density lipoprotein
LLN	Lower limit of normal
Life-threatening AE	Any adverse event that places the participant, in the view of the investigator, at immediate risk of death from the reaction when it occurred (ie, it does not include a reaction that would have caused death if it had occurred in a more severe form).
NA	Not applicable
Participant ID	The identification number assigned to a study participant which is used to track study-related documentation, including any reported AEs.
PR Interval	The interval between the beginning of the P wave and the beginning of the QRS complex of an electrocardiogram that represents the time between the beginning of the contraction of the atria and the beginning of the contraction of the ventricles
PT	Prothrombin time
PTT	Partial thromboplastin time
QTc Interval	The measure of time between the onset of ventricular depolarization and completion of ventricular repolarization corrected for ventricular rate.
RBC	Red blood cell
SI	Standard international unit
ULN	Upper limit of normal
Usual Social & Functional Activities	Activities which adults and children perform on a routine basis and those which are part of regular activities of daily living, for example: Adults: Adaptive tasks and desirable activities, such as going to work, shopping, cooking, use of transportation, or pursuing a hobby. Young Children: Activities that are age and culturally appropriate, such as social interactions, play activities, or learning tasks.
WBC	White blood cell
WHO	World Health Organization
WNL	Within normal limits

OPC-167832

Study 323-201-00007

Introduction

The Division of AIDS (DAIDS) oversees more than 300 clinical trials domestically and internationally, which evaluate the safety and efficacy of therapeutic products, vaccines, and other preventive modalities. Adverse event (AE) data collected during these clinical trials form the basis for subsequent safety and efficacy analyses of pharmaceutical products and medical devices. Incorrect and inconsistent AE severity grading can lead to inaccurate data analyses and interpretation, which in turn can impact the safety and well-being of clinical trial participants and future patients using pharmaceutical products.

Over the years, DAIDS scientific knowledge and experience have expanded, necessitating revisions of the DAIDS grading table which serves as a guide for assessing the severity of AEs (including clinical and laboratory abnormalities) in participants enrolled in DAIDS-sponsored and -supported clinical trials. The *Division of AIDS (DAIDS) Table for Grading the Severity of Adult and Pediatric Adverse Events, Corrected Version 2.1 (July 2017)* updates and replaces version 2.1 (March 2017).

DAIDS is grateful to the DAIDS Grading Table Working Group, numerous government and non-government affiliated medical subject matter experts and reviewers who were instrumental in the revision of the DAIDS grading table.

Instructions for Use

General Considerations

The *Division of AIDS (DAIDS) Table for Grading the Severity of Adult and Pediatric Adverse Events, Version 2.1* consists of parameters, or AEs, with severity grading guidance that are to be used in DAIDS clinical trials for safety data reporting to maintain accuracy and consistency in the evaluation of AEs. The term “severe” is not the same as the term “serious” in classifying AEs. The severity of a specific event describes its intensity, and it is the intensity which is graded. Seriousness, which is not graded, relates to an outcome of an AE and is a regulatory definition.

Clinical sites are encouraged to report parameters in the DAIDS grading table as they are written to maintain data consistency across clinical trials. However, since some parameters can be reported with more specificity, clinical sites are encouraged to report parameters that convey additional clinical information. For example, diarrhea could be reported as neonatal diarrhea; seizures, as febrile seizures; and pain, as jaw pain.

OPC-167832

Study 323-201-00007

The DAIDS grading table provides an AE severity grading scale ranging from grades 1 to 5 with descriptions for each AE based on the following general guidelines:

- Grade 1 indicates a mild event
- Grade 2 indicates a moderate event
- Grade 3 indicates a severe event
- Grade 4 indicates a potentially life-threatening event
- Grade 5 indicates death (*Note: This grade is not specifically listed on each page of the grading table*).

Other points to consider include:

- Use age and sex values as applicable.
- Unless noted, laboratory values are for term neonates. Preterm neonates should be assessed using local laboratory normal ranges.
- Where applicable, Standard International (SI) units are included in italics.

Selecting and Reporting a Primary AE Term

When selecting a primary AE term to report, sites should select the term that best describes what occurred to the participant. For example, a participant may present with itching, urticaria, flushing, angioedema of the face, and dyspnea. If the underlying diagnosis is determined to be an acute allergic reaction, sites should report “Acute Allergic Reaction” as the primary AE term.

Primary AE terms should be reported using the DAIDS Adverse Experience Reporting System (DAERS) only if they meet expedited reporting criteria. However, all primary AE terms should be reported using protocol-specific case report forms (CRFs). Because the reported information is stored in different databases (ie, safety and clinical), sites should report primary AE terms using the same terminology for data consistency.

When reporting using DAERS, other clinically significant events associated with a primary AE term that more fully describe the nature, severity, or complications of the primary AE term should be entered in the “Other Events” section. However, the severity grade for these events must be lower than or equal to the severity grade of the primary AE term. In the example above, dyspnea and angioedema of the face may be entered in the “Other Events” section, because they are more descriptive and provide additional information on the severity of the acute allergic reaction. However, their severity grades must be lower than or equal to the severity grade of the primary AE term of “Acute Allergic Reaction”.

OPC-167832

Study 323-201-00007

Differences exist in the reporting and recording of information (eg, signs and symptoms, clinically significant events) in DAERS and CRFs. Therefore, sites should refer to their protocols and CRF requirements for further instructions.

Grading Adult and Pediatric AEs

When a single parameter is not appropriate for grading an AE in both adult and pediatric populations, separate parameters with specified age ranges are provided. If no distinction between adult and pediatric populations has been made, the listed parameter should be used for grading an AE in both populations.

Reporting Pregnancy Outcomes

In the *Pregnancy, Puerperium, and Perinatal* section, all parameters are pregnancy outcomes and should be reported using the mother's participant ID. If an infant is not enrolled in the same study as the mother, any identified birth defects should be reported using the mother's participant ID. However, if an infant is enrolled in the same study as the mother or in another study, any identified birth defects should be reported using the infant's participant ID. Sites should refer to the applicable network standards for reporting abnormal pregnancy outcomes on the CRFs.

Determining Severity Grade for Parameters between Grades

If the severity of an AE could fall in either one of two grades (i.e., the severity of an AE could be either grade 2 or grade 3), sites should select the higher of the two grades.

Laboratory Values

General

An asymptomatic, abnormal laboratory finding without an accompanying AE should not be reported to DAIDS in an expedited timeframe unless it meets protocol-specific reporting requirements. Sites should refer to the applicable network standards for reporting abnormal laboratory findings on the clinical case report forms.

Values Below Grade 1

Any laboratory value that is between the ULN and grade 1 (for high values) or the LLN and grade 1 (for low values) should not be graded or reported as an AE. Sites should consult the *Manual for Expedited Reporting of Adverse Events to DAIDS, Version 2.0* and their protocol when making an assessment of the need to report an AE.

Overlap of Local Laboratory Normal Values with Grading Table Ranges

When local laboratory normal values fall within grading table laboratory ranges, the severity grading is based on the ranges in the grading table unless there is a protocol-specific grading criterion for the laboratory value. For example, "Magnesium, Low" has a

OPC-167832

Study 323-201-00007

grade 1 range of 1.2 to < 1.4 mEq/L, while a particular laboratory's normal range for magnesium may be 1.3 to 2.8 mEq/L. If a study participant's magnesium laboratory value is 1.3 mEq/L, the laboratory value should be graded as grade 1.

